#### • Medication Electronic Monitoring (MEMS) devices:

These will be used to assess medication utilization and adherence rates. They are Bluetooth enabled caps that fit on standard medicine bottles and record participants' medication utilization. Participants will be dispensed their opioid medication by the pharmacy in the MEMS equipped containers and informed to return their bottle at their next follow up visit.

#### • Defense and Veterans Pain Rating Scale (DVPRS):

The DVPRS is a validated pain assessment tool used to measure the degree to which pain influenced a respondent's ability to function over the prior 24 hours. The DVPRS incorporates a numerical rating scale, as well as functional word descriptors, color coding, and pictorial facial expressions matched to pain levels. DVPRS average pain scores can range from 0, "no pain," to 10, "as bad as it could be, nothing else matters." The DVPRS is used to assess current pain, average pain, and worst pain over the prior 24 hours. The DVPRS includes four supplemental questions examining how pain

impacts activity, sleep, mood, and stress on a numeric scale. Collectively, the DVPRS advances pain assessments beyond traditional 0-to-10 pain intensity scores and toward a better understanding of the impact pain has on an individual.

#### • Discharge data:

Inpatient morphine equivalents (24 hours prior to discharge), average pain score (24 hours prior to discharge), discharge pain medications prescribed, discharge morphine equivalents prescribed, hospital length of stay and discharge disposition.

- Actigraphy based sleep and activity data (e.g. average hours of sleep, average daily steps): Study participants will be provided with a wrist actigraphy device to wear during their hospitalization and throughout their recovery until their 2-week follow up appointment with the surgical team. Participants will return their actigraphy devices at the 2-week follow up appointment or be provided a pre-paid envelope to take home and mail back the device after the visit. Wrist actigraphy is a valid and objective tool to measure activity patterns and sleep-related parameters, which has been used in patient populations with both acute and chronic pain. Actigraphy data includes objective quantitative measures of sleep, such as total sleep time, sleep latency, fragmentation, wake after sleep onset, and sleep efficiency. Additionally, activity level is also captured using wrist actigraphy, including total activity time, steps, physical activity intensity, and total energy expenditure. Participants will receive, and be trained on how to wear, a screen-less actigraphy device on their wrist (GT3XP-BTLE, Actigraph, LLC, USA). Devices will be set to record in 30-second epochs at a medium sensitivity level for scoring sleep and wake time. Wear time validation will be accomplished using the Choi algorithm, as it more accurately estimates time worn accounting for forward and backward motions. The sleep data will be computed using the Cole-Kripke algorithm, which accurately distinguishes sleep from wakefulness approximately 88% of the time. Metabolic equivalent of tasks and energy expenditure will be measured with the Freedson algorithms. By uniquely pairing actigraphy data with PROMIS patient-reported pain, sleep, and physical function measures, this study will be one of the first to provide a robust analysis of sleep quality and activity in tandem to pain presentations in adult surgical patient populations during hospitalization and throughout immediate post-discharge recovery following surgery. These research efforts adhere to recommended best practices for using actigraphy to examine health outcomes.35
- Patient Assessment of Constipation Symptoms (PAC-SYM): This questionnaire is a 12-item self-report instrument divided into abdominal, rectal and stool domains. Across 12 items participants report their discomfort related to constipation ranging from 0, never, to 4, always. A total score is computed based on the average of all 12 items.
- Field notes and participant quotes:

Field notes are widely recommended in research as a means of documenting needed contextual information and accurately capturing participants' statements in real time. As such study staff will transcribe notes on their encounters with research participants, including summary of interaction and representative quotes from participants.

The LCS will work with the patient to create a pain management plan focused on behavioral education. The LCS interventions can encompass all, but not limited to, the information included below:

- Opioid Risk Education
  - o Patients will be provided with education about substance misuse and the opioid epidemic
  - o Patients will be educated by the LCS on safe methods for disposal of unused pain medications
- Therapeutic Intervention
  - o Patients will be provided with alternative non-pharmaceutical pain management options
  - Breathing techniques
  - Guided imagery

- o Progressive muscle relaxation
- o The Community Resiliency Model
  - Tracking
  - Resourcing
  - Grounding
  - Gesturing
  - Shift and Stay
  - Help Now!
- o Hospital-approved essential oil therapy
- o Motivational Interviewing
- o Reflective Listening
- Clinical Pain Coordination
  - The LCS team will work closely with the [name] as well as pain specialists [name], Co-Director of the acute pain service at Grady and [name], Director of the Medication Assisted Opioid Therapy Clinic.
  - LCS will complete the Behavioral pain assessment tool. The Checklist of Nonverbal Pain Indicators (CNPI) is a quick behavioral assessment used by clinicians to assess nonverbal indicators of potential pain patients are in such as grimacing, bracing, rubbing, and restlessness at rest and when moving.

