#### **Study Procedures/Assessments:**

Potential patients will be identified during the daily orthopaedic trauma morning report. Eligibility will be determined by the clinical research coordinator (CRC).

If the patient meets inclusion criteria, he/she will be approached by the CRC, and if informed consent is obtained, they will be enrolled into RedCAP for randomization into Group 1 (non- LCS) or Group 2 (LCS). After consenting, enrolling, and allocation, research staff will administer a battery of measures on tablets stored in RedCap, or on paper and later transcribed into REDCap to all participants (See Table).

Each day throughout hospitalization, the average pain score over the past 24-hours will be recorded via the nursing staff. During their follow up visits with the surgical team at Grady Hospital scheduled at 2-weeks, 6-weeks, and 3-months postoperatively participants will again be provided a tablet to complete outcome measures. In the event participants cannot physically travel to the clinic, appointments will be conducted over video conferencing and participants will have the option to be emailed the outcome measures to complete. If they are unable to complete the measures via email within 72-hours study staff will call participants to complete measures over the phone. If no response, paper copies of the measures will be mailed to participants with prepaid postage to return them.

The following data will be collected on the patients:

- Demographics:
  - Name, date of birth, date of admission, gender, ethnicity, body mass index.
- Trauma registry data:
  - Data abstraction that is completed by a separate quality team contained within the trauma department. i.e., injury severity score, mechanism, drug screen on arrival, alcohol screen, pre-existing conditions, inpatient complications.
- Comprehensive social determinants of health (SDOH) survey:
  - Includes assessments of: housing, financial stability, education, community context, intimate partner violence, health literacy, prior personal and family substance use, a validated measure of post-traumatic stress disorder, adverse childhood experiences, and mental illness. This has been utilized in prior research by this team and takes approximately 20-25 minutes to complete (attached).

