#### VISIT SCHEDULE AND ASSESSMENTS

Assessment	Visit 1:	Visit 2:	Visit 3:	Visit 4:
	Inpatient	2 Weeks (±	6 Weeks (±	3 Months (±
	Hospitalization	7 days)	14 days)	14 days)
Demographics	X			
Trauma registry data	X			
Comprehensive Social Determinants of Health (SDOH) Survey	X			
Revised Opioid Risk Tool (ORT)	X			
Short Form 36 Health Survey Questionnaire (SF-36)	X			X
Pain Management Questionnaire (PMQ)	X	X	X	X
Prescription Drug Use Questionnaire (PDUQ)	X	X	X	X
PTSD Screener	X			X
PROMIS: Sleep Disturbance	X	X	X	X
PROMIS: Physical Function	X	X	X	X
PROMIS: Pain Interference	X	X	X	X
PROMIS: Prescription Pain				X
Medication Misuse				
Opioid Literacy Tool (OLT)	X			X
Patient Satisfaction Survey		X		
Naloxone Questionnaire		X	X	X
PAC-SYM	X	X	X	
Inpatient Opioid Utilization (MME/day)	X			
Inpatient Numerical Rating Scale (NRS) Pain Score	X	X	X	X
Medication Electronic Monitoring (MEMS) devices:		X	X	X
Defense and Veterans Pain Rating Scale (DVPRS)	X	X	X	X

Inpatient Sleep Actigraphy	X				l
Field notes and participant quotes	X	X	X	X	l
Participant Compensation	X	X		X	ı

Questionnaires/surveys and meetings with the Life Care Specialist will occur during scheduled telehealth appointments. No charges will be generated specifically relating to the research components.

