Aim 2: Evaluate the effectiveness of Life Care Specialist intervention on reducing long-term postoperative opioid medication utilization. As described above, a systematic machine learning guided model construction approach will be used to also test the working hypothesis that participants in the intervention will report decreased utilization of opioid pain medications both in the inpatient and outpatient setting up to 3-months postoperatively. Separate mixed-effects models will be constructed to estimate differences in average MME/day during inpatient hospitalization as well as to estimate difference in average MME/day over every study follow up point up to 3-months postoperatively.

Aim 3: Explore the feasibility of utilizing actigraphy devices to capture postoperative functional outcomes among patients during their hospitalization and up to 2-weeks postoperatively following orthopaedic trauma. Generalized estimating equations (GEE) will be used to explore changes in functional outcomes over the 2-

week postoperative period. For example, activity will be measured as average step per day and sleep will be measured as average nightly sleep efficiency and duration. Separate GEE will be computed for each actigraphy related measure. In the event a significant change in any of the objective outcomes, a linear mixed-effect model will be constructed to ascertain any significant differences in actigraphy collected outcomes exist between participants in the intervention and the control arms over the two-week postoperative period.

Power: A sample of 200 provides 85% power ( $\alpha$ =0.05) to detect a difference as small as 0.5 in the mean pain score between the intervention arm and the controls using repeated measures mixed effects modeling (Power Analysis and Sample Size Software, NCSS, Kaysville, UT, USA). All analyses will be conducted in R (R Core Team, Vienna, Austria) by the Co-PI and his team at the Nell Hodgson Woodruff School of Nursing ([name]). The *glmnet* package will be used to determine which variables should be included in the regression models using a LASSO approach, the *lme4* package will be employed to compute final regressions and assess fit. Post hoc power analyses will be conducted when exploring differences in outcomes based on demographics (e.g., gender).

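### Actigraphy wear ends at a 2-week visit that may fall on any day from 7 to 21, so second-week coverage thins and the Aim 3 two-week trend is open to bias if visit timing is related to activity or recovery

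*Combined protocol and SAP*

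**What the plan says.** All references are to the combined protocol and SAP.

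- **Wear period** (Study Procedures/Assessments, actigraphy entry under Discharge data). Participants receive a wrist device "to wear during their hospitalization and throughout their recovery until their 2-week follow up appointment with the surgical team". On return, "Participants will return their actigraphy devices at the 2-week follow up appointment or be provided a pre-paid envelope" for mailing the device back after the visit. Nothing asks for wear beyond the visit.
- **Visit timing.** Study Procedures/Assessments has follow-up "scheduled at 2-weeks, 6-weeks, and 3-months postoperatively". The Visit Schedule and Assessments table gives Visit 2 a tolerance of 7 days either side of 2 weeks.
- **Analysis** (Statistical Analysis, Aim 3). The aim is the feasibility of capturing function "during their hospitalization and up to 2-weeks postoperatively following orthopaedic trauma". The method for the time trend comes next: "Generalized estimating equations (GEE) will be used to explore changes in functional outcomes over the 2" (the sentence goes on to name a fortnight after surgery). As examples, "activity will be measured as average step per day and sleep will be measured as average nightly sleep efficiency and duration". Then: "In the event a significant change in any of the objective outcomes, a linear mixed-effect model will be constructed"; its purpose is to compare the arms.
- **Not stated.** There is no fixed last day of wear, minimum number of valid days, common analysis window, time coding, working correlation, or handling of days lost to an early visit. A non-wear algorithm is named, but it does not set a common window.
- **Schedule row.** The visit table lists actigraphy as an inpatient item ticked at Visit 1 only, which does not match wear up to the 2-week visit.

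**The concern.** The analysis period is two weeks, but data collection stops on a day that varies between patients. A patient seen on day 10 gives nothing for days 11-14; one seen on day 14 or later can give the whole fortnight. The group still wearing the device therefore shrinks through the second week.

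This is harmless for bias if the visit day has nothing to do with activity, sleep or speed of recovery. A link is plausible, because steps per day measure mobility and mobility may affect when a patient attends. If there is a link, the estimated trend mixes real change within patients with change in who is still being measured. That trend is the first analysis of Aim 3, and its significance decides whether the arms are compared on actigraphy.

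**Working it through.** **1. Range of the last wear day.** Visit 2 is nominally day 14, with a tolerance of 7 days: 14 - 7 = day 7 and 14 + 7 = day 21.

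**2. Coverage.** Share still wearing on day d = P(visit day ≥ d). The plan gives no visit-day distribution, so these are assumed, with wear from day 1 and all visits within the window.

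- *Uniform over days 7-21 (15 days).* Days 8 to 14 are covered 14/15, 13/15, 12/15, 11/15, 10/15, 9/15 and 8/15. The mean is 77/(15 × 7) = 73%. Day 14 is covered 8/15 = 53%, so 7/15 = 47% of patients lack some part of the fortnight.
- *Normal around day 14, rounded to whole days.* Coverage of day d = 1 - Φ((d - 0.5 - 14)/SD), with visits outside the window set to its edges.
  - SD 2: 0.999, 0.997, 0.988, 0.960, 0.894, 0.773, 0.599 for days 8 to 14. The mean is 6.21/7 = 89%, and 40% lack the full fortnight.
  - SD 4: 0.948, 0.915, 0.870, 0.809, 0.734, 0.646, 0.550. The mean is 5.47/7 = 78%, and 45% lack the full fortnight.

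**3. Effect on the trend (simulation).** Assumptions: 200 patients, GEE linear in day over days 1-14 with robust standard errors, between- and within-patient SD 1500 steps, visit-day SD 3. The range given is across repeated sets of runs.

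| Setting | Independence GEE | Exchangeable GEE |
|---|---|---|
| True trend 0, timing unrelated to outcome | 3-6% false trends | 3-6% |
| True trend 0, more active patients seen earlier, correlation 0.3 | 45-48%; false fall about 220-230 steps over days 1-14 | 3-8% |
| Same, correlation 0.5 | 88-92%; false fall about 385-400 steps | 5-8% |
| True mean slope 100 steps/day, slope SD 100, faster recoverers seen earlier, correlation 0.3 | returns about 85 | about 91 |
| Same, correlation 0.5 | about 73 | about 83-84 |
| Fixed 14-day wear | 5-6% false trends when the true trend is 0; true slope 100 returned as 99-101 | same |

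The independence slopes are the least stable figures: values as low as 80 and 65 were also obtained. A random-slope mixed model on the same kind of data returned 94 and 93, so it reduces the attenuation without removing it.

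A separate simulation on a standardised scale (intraclass correlation 0.5, mean slope zero, slope SD 0.03 per day) linked timing to rate of recovery at correlations 0.3-0.5. False trends appeared in 17-51% of runs under independence and 11-35% under exchangeable. The exchangeable structure therefore protects well when timing follows a patient's level, and less well when it follows the rate of recovery.

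**4. Arm comparison.** In the slope-100 setting, with visit timing handled alike in both arms, the arm-by-day difference averaged about 0 (-1.4 to +1.4 steps/day). The overall trend was significant in every run, so the condition for comparing arms was met either way.

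**The case against.** - **Coverage is not lost wholesale.** A reader might infer that second-week data come only from patients seen late. They do not: any visit on days 8-13 contributes part of the second week, and only a day-7 visit contributes none. Some of the 40-47% without a full fortnight miss just a day or two. This stands.
- **The link with mobility is undocumented.** Study Procedures/Assessments offers video appointments to those who cannot travel, so poor mobility need not shift the visit date. The window is a tolerance, not a distribution, and uniform timing is an extreme case. This stands, and it makes the bias conditional.
- **The high error rates need an independence working correlation and no true trend.** The plan names no working correlation, and some recovery after trauma surgery is plausible. This stands, but so does the converse: the choice that separates a near-nominal error rate from about 90% in the worst setting is left open.
- **Daily indexing is assumed.** Aim 3 speaks of averages, and an analysis by period would lose less to early visits.
- **The arms are randomised.** A reader might infer that the arm comparison is biased because the intervention could change attendance. No passage supports this. The 2-week visit is with the surgical team, and Study design and methods says contact with the usual providers is the same.
- **Aim 3 is exploratory feasibility work in a pilot.** Pain and opioid results are untouched.

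What remains is a collection rule whose end day does not match the analysis period and may be related to the outcome.

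**Conclusion.** The point holds in conditional form and should be addressed. Wear ends on a day between 7 and 21 while the analysis covers two weeks, so second-week coverage thins to an average of 73% (uniform visit days) or 78-89% (normal, SD 2-4), assuming wear from day 1. The protocol states no start day for wear relative to surgery, so even first-week coverage is an assumption.

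If timing is unrelated to outcome, the cost is precision only. If it is related, the Aim 3 trend can be biased: an independence GEE then shows false trends in about half to nine-tenths of trials at assumed correlations of 0.3-0.5 with activity level. Where timing follows recovery slope, a true slope of 100 is returned as about 91-83 (exchangeable) or 85-73 (independence). The SDs, slopes and correlations are all assumptions; the documents offer no data on any of them.

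It would go too far to say that the trend will be wrong, that the decision to compare arms will be driven by an artefact, or that the arm comparison is biased. None of these is shown.

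**What to change.** 1. In the actigraphy entry, replace the rule that ends wear at the 2-week appointment with wear through postoperative day 14 whatever the visit date. Patients seen earlier keep the device on and return it in the pre-paid envelope already provided. This is the essential change, because it removes the visit-timing mechanism for patients who comply.
2. In Statistical Analysis, Aim 3, index actigraphy by day since surgery and restrict the analysis to days up to 14.
3. As a secondary safeguard, avoid an independence working correlation, or estimate the trend with a linear mixed model with participant random intercept and slope. The latter would be a new specification: Aim 3 gives no random-effects structure for its mixed model, and the model reduces rather than removes bias from early device return.
4. Reconcile the visit table, which lists actigraphy as inpatient at Visit 1 only, with the wear period in the text.

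The cost is up to 7 more days of wear for patients seen early, some more mailed returns and device loss, and protocol and SAP wording. No extra visits are needed.

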#### VISIT SCHEDULE AND ASSESSMENTS

Assessment	Visit 1:	Visit 2:	Visit 3:	Visit 4:
	Inpatient	2 Weeks (±	6 Weeks (±	3 Months (±
	Hospitalization	7 days)	14 days)	14 days)
Demographics	X			
Trauma registry data	X			
Comprehensive Social Determinants of Health (SDOH) Survey	X			
Revised Opioid Risk Tool (ORT)	X			
Short Form 36 Health Survey Questionnaire (SF-36)	X			X
Pain Management Questionnaire (PMQ)	X	X	X	X
Prescription Drug Use Questionnaire (PDUQ)	X	X	X	X
PTSD Screener	X			X
PROMIS: Sleep Disturbance	X	X	X	X
PROMIS: Physical Function	X	X	X	X
PROMIS: Pain Interference	X	X	X	X
PROMIS: Prescription Pain				X
Medication Misuse				
Opioid Literacy Tool (OLT)	X			X
Patient Satisfaction Survey		X		
Naloxone Questionnaire		X	X	X
PAC-SYM	X	X	X	
Inpatient Opioid Utilization (MME/day)	X			
Inpatient Numerical Rating Scale (NRS) Pain Score	X	X	X	X
Medication Electronic Monitoring (MEMS) devices:		X	X	X
Defense and Veterans Pain Rating Scale (DVPRS)	X	X	X	X

Inpatient Sleep Actigraphy	X				l
Field notes and participant quotes	X	X	X	X	l
Participant Compensation	X	X		X	ı

Questionnaires/surveys and meetings with the Life Care Specialist will occur during scheduled telehealth appointments. No charges will be generated specifically relating to the research components.

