- The LCS will provide local, state, and national resources to enhance the whole health aspect of the position. These resources include but are not limited to: written documents that outline the key concepts of the pain management techniques taught by the LCS and a list of hotlines and websites.
- LCS, when applicable, will provide education for caretakers on the risk of opioid use and the non-pharmaceutical pain management protocol.
- LCS will provide follow up for all patients in intervention group.

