#### **Data and Safety Monitoring and Reporting:**

The Life Care Specialist (LCS) and/or study personnel will respond to study patients to employ behavioral and non-pharmacologic strategies that are designed to decrease opioid utilization, improve pain control via alternative techniques, and educate patient on pain management. Enrolled patients will receive support, direct connection to resources, and follow-up with the LCS during their participation in the program. The patients enrolled in the intervention arm of the RCT will receive direct support and regular follow up with the LCS in obtaining necessary services and ensuring an appropriate level of education is met.

There will be no direct intervention other than education, mentoring, and advocacy on behalf of the patient by study personnel therefore minimizing risk of misusing prescriptions.

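### The protocol gives two conflicting accounts of how follow-up outcomes are collected, and one permits, without stating it, that only intervention patients answer in or right after a session with their pain coach

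*Combined protocol and SAP*

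**What the plan says.** The sentence below the table in Visit Schedule and Assessments reads "Questionnaires/surveys and meetings with the Life Care Specialist will occur during scheduled telehealth appointments". It states no exception.

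Study Procedures/Assessments describes something else. At the surgical team's 2-week, 6-week and 3-month visits at the hospital, "participants will again be provided a tablet to complete outcome measures". Video is a fallback: "In the event participants cannot physically travel to the clinic, appointments will be conducted over video conferencing", with the measures offered by email. If the emailed measures are not completed within 72 hours, "study staff will call participants to complete measures over the phone", and paper copies are mailed if there is no response. At baseline, "research staff will administer a battery of measures on tablets stored in RedCap" or on paper.

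Contact with the LCS belongs to one arm. The list of LCS responsibilities in Introduction and Background says "LCS will provide follow up for all patients in intervention group", and Data and Safety Monitoring and Reporting says "The patients enrolled in the intervention arm of the RCT will receive direct support and regular follow up with the LCS".

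**The concern.** The first problem is practical. Staff who follow the schedule note would collect follow-up questionnaires by telehealth as routine. Staff who follow the procedures section would do so only for patients who cannot travel. The mode of collection would then depend on which page was read.

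The second problem is comparability. The note puts questionnaires and LCS meetings in one sentence with one setting, and only intervention patients have LCS meetings. One natural way to carry it out is a single appointment in which an intervention patient meets the coach and answers the questionnaires, while a control patient only answers. The LCS coaches patients on pain and aims to lower their opioid use. The affected measures are self-reports of pain, function, medication misuse and opioid knowledge, and the protocol describes neither blinding nor an independent assessor. Answers on pain and misuse may shift when the coach is near. The Opioid Literacy Tool covers content the LCS teaches, so completing it just after a session would partly measure short-term recall.

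If the conditions of reporting differ by arm, they are confounded with arm. No covariate, LASSO selection or random effect in the Statistical Analysis section can remove that.

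**Working it through.** **1. Mode of collection, side by side**

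| Source | Default at follow-up | Telehealth |
|---|---|---|
| Visit Schedule and Assessments, note | Telehealth appointment | Always |
| Study Procedures/Assessments | Tablet at clinic visit | Only if the patient cannot travel |
| MEMS entry | Bottle returned at next follow-up visit | Not mentioned |
| Actigraphy entry | Device returned at the 2-week visit, or mailed back after it | Not mentioned |

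The two device entries fit the clinic-visit account. The schedule note also fits poorly with its own table, which places many questionnaires at Visit 1, the inpatient stay.

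**2. Who collects the data**

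The procedures section names research staff at baseline and study staff for phone completion. No text has the LCS administer, attend or see the follow-up questionnaires. No text excludes it, and study staff is not defined.

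**3. Which outcomes could be touched**

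- Self-reported at all three follow-up visits: PMQ, PDUQ, DVPRS, and PROMIS Sleep Disturbance, Physical Function and Pain Interference.
- Self-reported at 3 months: PROMIS medication misuse and the Opioid Literacy Tool. At 2 weeks: patient satisfaction.
- Not affected: inpatient NRS recorded by clinical staff, and MME taken from the health record.

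**4. What an assumed shift would do (illustration only)**

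Inputs from the Power paragraph: 200 patients (100 per arm, from Study design and methods), difference 0.5 points, power 85%, alpha 0.05, taken here as two-sided. SD, within-patient correlation, number of repeats and dropout are not given, so the 85% cannot be reproduced. It can only be inverted.

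- Lower SE, implied by the power claim: 0.5 / (1.96 + 1.036) = 0.167. For a single comparison this means SD = 0.167 / √(2/100) = 1.18.
- Upper SE, assuming SD 2 and one measure per patient: 2 × √(2/100) = 0.283.
- Repeated measures at SD 2 fall between these. The factor √((1 + (m − 1)ρ)/m) with m = 3 or 4 and ρ = 0.3 to 0.7 runs from √(1.9/4) = 0.689 to √(2.4/3) = 0.894, giving SE 0.195 to 0.253.

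With no true effect and a reporting shift b in one arm, the two-sided rejection rate is 1 − Φ(1.96 − b/SE) + Φ(−1.96 − b/SE).

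| b (assumed) | SE 0.167 | SE 0.283 |
|---|---|---|
| 0 | 5% | 5% |
| 0.20 | 22% | 11% |
| 0.25 | 32% | 14% |

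The value 0.25 is half the target difference. The formula is symmetric, so a shift in either direction gives the same rate. It applies b to the whole pain contrast. If inpatient NRS enters the same model, a shift confined to follow-up is diluted and the rates are lower.

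**The case against.** A reader might infer that the LCS sits in on outcome collection, or that questionnaires and coaching share one appointment. The documents do not support that as a statement of fact. The sentence has a compound subject and a plural, so it can mean only that both activities use telehealth. The sentence after it concerns charges, which suggests a logistics note. The procedures section gives collection to research or study staff, and the tablet, email and mail forms are self-completed. The Confidentiality section stores online answers as numbers without the question, with the key held only by investigators at the university. The LCS role is overseen by the partner non-profit. This weighs against exposure, but it does not rule it out.

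A reader might also infer that the bias must favour the intervention. That is not established. Trust in a coach could equally lead patients to disclose more pain or misuse. Patients may also know their arm wherever they answer, so separating the sessions would not remove all self-report bias.

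Finally, the false-positive rates rest on an assumed shift and on standard errors that the documents do not state. That is correct, and they should be read only as a range.

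What remains is that the two sections conflict, that LCS contact is in one arm only, and that no rule keeps the follow-up questionnaires apart from it.

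**Conclusion.** The conflict between the schedule note and the procedures section is certain from the text. The arm-dependent reporting condition is permitted, not stated, and the size and direction of any resulting bias are unknown. If a one-arm shift of 0.2 to 0.25 points is assumed on the self-reported pain contrast, a nominal 5% test would reject about 11% to 32% of the time under no effect, across standard errors from 0.283 down to 0.167. None of these figures is a prediction for this trial. The upper end takes the stated power at face value, and the lower end assumes an SD of 2 with a single measure. The missing SD is a separate matter and does not decide this point.

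The change is worth making because the problem can be prevented at collection and cannot be corrected in the analysis.

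**What to change.** Reconcile the two sections, limiting the change to the 2-week, 6-week and 3-month questionnaires:

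- In both arms, measures are completed through the sequence already in Study Procedures/Assessments (clinic tablet, then video with email, phone, mail).
- They are completed before any LCS contact at that time point and without the LCS present.
- Any phone completion is done by research staff other than the LCS.
- The mode actually used is recorded for each patient and visit, so that the arms can be compared on it.
- Questionnaires are removed from the sentence under the visit schedule, and what it says about LCS meetings is limited to follow-up after discharge, so that it does not contradict the inpatient LCS intervention.

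Inpatient measures, including the Opioid Risk Tool that the LCS uses, are left as they are.

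The cost is protocol wording and minor scheduling of the visit order. Existing research staff can do it.
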